1.2. Rationale and hypothesis

We propose a clinical trial in which 36 patients with synkinesis will be enrolled into one of two treatment arms: chemodenervation alone followed by dual therapy (i.e. add neuromuscular retraining), and neuromuscular retraining alone followed by dual therapy (i.e. with chemodenervation). In the absence of this clinical trial, patients seen at our center would be offered one or both treatments based on clinician judgment and patient preference, which is our current practice standard. At other major academic centers, however, chemodenervation may be the standard of care due to provider preference, training, or the lack of qualified retraining therapist. While many institutions use chemodenervation monotherapy routinely in their practice, high volume centers that publish research data on facial paralysis report both techniques. There is no published consensus or written guidelines on the treatment of synkinesis including choice of treatment, sequence of treatment, and timing to add dual

therapy. We hypothesize clinician-reported outcome measures will show statistically greater improvements for retraining therapy as compared to chemodenervation.

Chemodenervation has a rapid onset and has been shown to improve patient-reported outcomes; however, the effect is temporary usually requiring re-injection every three to four months as is the case with all conditions treated with injections. In contrast, neuromuscular retraining provides long lasting improved coordination among synkinetic facial muscles, but often does not provide patients with complete resolution of symptoms. Selective ipsilateral chemodenervation of synkinetic muscles can be used in conjunction with neuromuscular retraining therapy to provide a window of opportunity, in which the patient learns to practice isolated, coordinated movements without the co-contraction and restriction caused by synkinesis. While combined chemodenervation and therapy may result in optimal treatment, the efficacy, timing, and sequence of dual treatment still needs to be elucidated for patients with synkinesis.

In the first four months of the trial, we hypothesize that patients undergoing neuromuscular retraining therapy will achieve statistically greater improvements on clinician-reported outcome measures as compared to patients receiving chemodenervation. Patients may achieve the additional gains after combined treatments during the next four months of the trial. There may exist interesting differences in our secondary data collection of patient-reported measures and interview data after single and dual treatments.

2. Objectives

2.1. Primary outcome and endpoints

To determine improvement in physical functioning from baseline, we will look at the change on the clinician-reported Sunnybrook Facial Grading System (SFGS). The examination is routinely collected at clinic visits. At each clinic visit, patients will be videotaped as a part of routine care. However, patients in the study will undergo a blinded evaluation and SFGS scoring using the video by trained blinded clinicians not participating in their direct clinical care, to decrease observer bias.

2.2. Secondary outcomes and endpoints

To determine the physical/functional, social, and emotional burden of synkinesis and efficacy of treatment, qualitative analyses of patient interview data and patient-reported instruments will be used to assess the impact of synkinesis on patient's lives.

- SAQ and FaCE scores (disease specific patient-reported instruments routinely collected as part of clinical care)
- HADS and BIPQ scores (depression, anxiety, and illness perception patient-reported instruments)
- Themes, codes from interview transcripts (using qualitative research methods)

Interviews and SAQ and FaCE scores will be collected before treatment, after four months of treatment, and after eight months of treatment.

The HADS and BIPQ mental health instruments will be collected before and repeated after four months of treatment (as part of participation in Protocol 2015-0366) and eight months of treatment (as part of participation in this protocol).

To quantify the disruption in social functioning caused by synkinesis, participants will enroll in IRB Protocol 2015-0366 and complete a series of social functioning and mental health instruments, and emotion expression recognition tasks. Repetition of emotional expression recognition tasks after four

months of treatment may show improvement in recognition and emotional information interpretation; these tasks will not be repeated after eight months as no meaningful or statistical difference is anticipated at this time point.

SFGS, SAQ, and FaCE are all part of the standard treatment and follow up of patients with synkinesis. The only activities that will be conducted for research purposes are the qualitative interviews, the tasks in Protocol 2015-0366 (done before treatment and after four months of treatment, which include the HADS and BIPQ), and the HADS and BIPQ after 8 months of treatment (this protocol).

3. Study design

This study will compare chemodenervation with neuromuscular retraining. Both treatments are widely practiced in the United States for the treatment of synkinesis, and it is not known which is best.

Participant Identification and Eligibility:

Participants will be primarily identified from our University of Wisconsin *Facial Nerve Clinic*. While most patients with facial nerve paralysis recover in 3 months, patients with chronic facial paralysis may still benefit from spontaneous recovery of muscle function thereafter. Symptoms of synkinesis are often not displayed until 4 months with the display of aberrant facial muscle motions. Eligible patients will demonstrate synkinesis and had their onset of peripheral facial paralysis from any cause at least 4 months prior. Muscle function and synkinesis will be assessed using standard clinical evaluation tools.

Exclusion criteria: (1) under 18 years of age (2) previous treatment with reanimation surgery (except for those patients who underwent upper eyelid weight placement to aid in eye closure), (3) intolerance or contraindication to botulinum toxin injection, and/or (4) previous treatment for synkinesis with chemodenervation or neuromuscular retraining therapy (5) vulnerable populations such as known prisoners, pregnant/breastfeeding women, or subjects with impaired decision-making capacity, including those with severe psychiatric illnesses (6) individuals over 89 years of age

Pre-Treatment Screening and Testing: Pre-treatment activities will include clinical evaluation and clinician- and patient-reported instruments that are already standard of care (SFGS, SAQ, FaCE), a semi-structured interview, and the tasks included in IRB Protocol 2015-0366. Patients will be randomly assigned to one of two treatments; Arm 1: neuromuscular retraining therapy for four months, with chemodenervation added thereafter, or Arm 2: Botox/chemodenervation for four months, with neuromuscular retraining therapy added thereafter. Allocation schedule will not be known to clinicians prior to consenting.

Blinding: Research team members who will score the videos will be blinded. The physician conducting the initial clinic visit will be blinded to the patient's treatment arm until after they have been enrolled. The physician providing treatment, interviewer, and study coordinator will not be blinded to the participant's treatment arm.

Treatment and follow-up: Treatment will be performed using standard techniques in all patients. All patients will be followed by providers approximately once per month for either neuromuscular retraining therapy or botulinum toxin injection/injection evaluation over the phone, per routine clinical care. Follow-ups will provide preliminary data on treatment outcomes. Patients will also complete the SAQ and FaCE at each visit, and one month after chemodenervation as per routine protocol. Patients will undergo interviews (and tasks entailed in IRB Protocol 2015-0366) after 4 months of treatment, to determine the effects (if any) of treatment on physical, social, and emotional burden.

Patients will undergo dual therapy for four months after the initial four months. They will continue to complete the SAQ and FaCE at each care visit and will be asked to complete a qualitative interview and BIPQ and HADS instruments after 8 months of treatment.

It can be difficult to coordinate interviews with regularly scheduled patient visits. If the study team is unable to schedule these procedures on the same day, the subject will be given the option of returning on a different day of their choosing. If there are extenuating circumstances, the subject may complete the interview over the phone or via video conferencing software called WebEx. The research-only evaluations do not affect clinical care for patients.

At each time point (pre-treatment, after 4 months of treatment, and after 8 months of treatment), a trained interviewer who is not a member of the clinical staff will conduct a semi-structured qualitative interview. We will invite everyone to interview, with the goal of at least 24 patients completing interviews before treatment and after 4 months of treatment. The interview at 8 months will be optional. Interview guides were developed in consultation with clinical staff and piloted prior to use; guides include both prompted and unprompted open-ended questions aimed at understanding patient experience with various aspects of synkinesis and treatment. All interviews will be transcribed verbatim and any identifiers will be removed from transcripts prior to coding. Data will be coded using a catalogue of codes developed through analysis of emergent themes in a subset of interview transcripts. The Qualitative Core in the Wisconsin Surgical Outcomes Research Program will assist with data collection and analysis associated with qualitative aims.

The interview recordings will be transcribed by trained transcriptionists employed through the Wisconsin Surgical Outcomes Research Program (WiSOR) or an outside contractor with a business associate agreement that has been approved by UW Legal Services/Privacy Officer for HIPAA compliance. Transcriptionists have been instructed to remove identifying information from the transcripts. The audio recordings and transcripts will be shared through a secure server that only the transcriptionists and study team members have access to.

The completed interview transcripts will be stored on the secure network within the Wisconsin Surgical Outcomes Research Program (WiSOR). The main levels of security for this data application server housed at the SMPH Computer Center include being securely located behind the UW-Madison campus firewall, having data directory access controls, having physical server security, and having virtual server security. The participants' names and identifying information will be stored separately from the interview transcripts. The only link between the transcripts and the identifying information will be a subject identification number contained in both data files.

4. Study population

4.1. Inclusion criteria

Each patient must meet all of the following inclusion criteria to be enrolled in the study.

1. Has ipsilateral synkinesis of facial muscles
2. It has been at least four months since their onset of peripheral facial paralysis from any cause
3. Age 18 or older
4. Ability to read and write in English

4.2. Exclusion criteria

Patients meeting any of the following exclusion criteria are not to be enrolled in the study.

1. Under 18 years of age
2. Previous treatment with reanimation surgery (except for upper eyelid weight placement)
3. Intolerance or contraindication to botulinum toxin injection
4. Previous treatment for synkinesis with chemodenervation or neuromuscular retraining therapy
5. Pregnant and/or breastfeeding women
6. Patients with impaired decision-making capacity, including those with severe psychiatric illnesses
7. Individuals over 89 years of age

4.3. Protected populations

We will not be including any vulnerable populations, such as children, prisoners, those without decision making capacity or women known to be pregnant in this study.

5. Trial interventions

The intervention portion of this study is the assignment to Treatment Arm 1 or Treatment Arm 2.

5.1. Treatment Arm 1 (Neuromuscular retraining therapy)

Neuromuscular retraining therapy alone for four months, with botulinum toxin injection added during an additional four month period.

5.2. Treatment Arm 2 (Chemodenervation)

Ipsilateral chemodenervation with botulinum toxin injections alone for four months (onabotulinumtoxinA/Botox, Allergan or incobotulinumtoxinA/Xeomin, Merz), with neuromuscular retraining therapy added for an additional four months. Prior authorization for therapy will be done through normal clinical protocols as routine patient care.

OnabotulinumtoxinA/Botox is the preferential choice of neurotoxin, unless this is not allowed by the patient's insurance carrier in which case incobotulinumtoxinA/Xeomin will be utilized. The UW Pharmacy and Therapeutics Committee has evaluated the two and determined them to be equivalent for this and other treatments. Prior authorization for drug injection will be done through normal clinical protocols as routine patient care.

5.3. Allocation to intervention

Participants will be randomized to each treatment arm with equal probability (1:1 randomization) using a computerized random number generator with random block size (all study personnel except the statisticians are blinded to block size). The randomization assignment will be revealed to the unblinded study coordinator after consent. The clinicians will be blinded to the treatment until the end of clinic.

6. Participant recruitment and consent

6.1. Participant identification

We will recruit patients from the University of Wisconsin *Facial Nerve Clinic*.

6.2. Screening

UW Health physicians who treat facial nerve disorders, will assess patient eligibility. Departments of Surgery, Otolaryngology, Neurosurgery, and Neurology and therapists in the Department of Orthopedics and Rehabilitation, will identify patients who meet the study requirements. All protected health information used during the screening process of a potential participant will be the minimum necessary for the conduct of this study. Any protected information recorded will be destroyed at the end of the

screening process unless the patient enrolls. The clinical care team of the potential participant will be aware of the potential participation in this study as they will be the ones who refer the participant.

6.3. Recruitment and consent

The human subjects participating in this study will be recruited from the University of Wisconsin *Facial Nerve Clinic*. After physicians identify eligible patients and introduce available treatments, they will ask if the patient is interested in speaking to a study coordinator. A study coordinator will then offer enrollment in both IRB protocol 2015-0366 and this protocol. In clinics where the study coordinator is not available, patients will be given an information sheet, flowchart, and consent form describing the study during the patient's visit at UWHC and told that the coordinator will call within the week to explain the study.

A participant's decision whether or not to participate will not affect the care received as a patient. Participants will be treated according to the standard of care until consent for the study is obtained. Participants must meet inclusion and exclusion criteria as listed above. Participants will be selected without consideration of socio-economic background, however if their insurance status precludes them from coverage for therapy and/or Botox they will need to pay out of pocket. If they are unwilling/unable to do this, we will not enroll them in the study as their treatment with only the treatment covered by insurance would not be truly random.

Following explanation of the consent form, each potential participant will be given an opportunity to read it thoroughly. Before being allowed to sign the consent form, potential participants also will be given an opportunity to ask questions. The investigator will emphasize the fact that the participant can terminate involvement at any time without any consequences. Once the consent form has been signed, the study pre-treatment procedures will be performed if not already captured in the medical record.

A participant is enrolled prior to treatment and will undergo baseline evaluations. They will be randomized on the day of their initial clinic visit.

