6.4. Compensation

We will provide \$25 for each semi-structured interview before treatment, after four months, and after eight months of treatment for a potential total of \$75. This is in addition to compensation for completion of tasks of protocol 2015-0366 which are \$25 for emotion testing before treatment and again after four months.

7. Activities and measurements

Enrollment: Participants will be enrolled after signing the informed consent form.

Pre-treatment visit: During the initial visit, the multi-disciplinary clinical team (therapist and surgeon) will provide education on eye care and avoidance of other therapies that could worsen the synkinesis before treatment is initiated (e.g. maximal effort exercises), and describe treatment with neuromuscular retraining therapy and chemodenervation with botulinum toxin injections. Both treatments are standards of care and will be presented without bias as options. After the clinical evaluation, the Study Coordinator will offer study enrollment, obtain consent and assign cohort based on randomization. We will use a predetermined and blind randomization sequence designed independently by the study biostatistician.

		per standard protocol			
Time Window	6 weeks-24 hours before treatment	Four months	After four months	Four months	After four months of dual therapy
Facial Clinimetric Evaluation (FaCE) Scale (10 min)	SOC	SOC	SOC	SOC	SOC
Sunnybrook Facial Grading System (SFGS)	SOC	SOC	SOC	SOC	SOC
Synkinesis Assessment Questionnaire (SAQ) (10 min)	SOC	SOC	SOC	SOC	SOC
Interviews (Audio Recorded) (60-90 min)	X		X		X
Psychological Assessments (HADS, BIPQ) (10 min)	E		E		X
Tasks from Protocol 2015-0366 (60-90 min)	E		E		

Procedure Key: **SOC** = performed as needed per Standard of Care; **X** = Research Only for this protocol; **E** = Research only for Protocol 2015-0366

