7.3. Participant withdrawals

Participants have the right to withdraw from the study at any time for any reason, either before or after treatment begins. Additionally, any participant may be discontinued from the study at any time at the discretion of the investigator if he or another provider feels it is in the best interest of the participant. If a participant withdraws or is withdrawn from one aim, they may continue to participate in the other aims.

Study participation may be terminated early under the following circumstances:

- (1) the participant does not meet all inclusion criteria and is deemed a screen failure
- (2) the participant meets any of the exclusion criteria and is deemed a screen failure
- (3) the participant does not adhere to protocol requirements (e.g., completing questionnaires, refusing permission to have interview recorded, etc.)
- (4) the participant experiences an AE which in the investigator's opinion requires their withdrawal from the study
- (5) the participant is lost to follow up
- (6) death of the participant

The study team will document the reason(s) for withdrawal of each participant in source documents.

Participants that withdraw or are withdrawn prior to treatment will be replaced. Their pre-treatment data may be used to establish baseline function for comparison. Participants that withdraw from any aspect of the study will continue to be cared for per the standard of care.

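### Coverage of both treatments need not be confirmed before allocation, and pre-treatment withdrawals are replaced, so an insurer's later refusal could select patients by arm

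*Combined protocol and SAP*

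**What the plan says.** The coverage rule is in section 6.3. It first offers a self-pay route: "if their insurance status precludes them from coverage for therapy and/or Botox they will need to pay out of pocket". For those unwilling or unable to do so it states: "we will not enroll them in the study as their treatment with only the treatment covered by insurance would not be truly random".

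The timing of allocation is given in three places:
- Section 6.3: "They will be randomized on the day of their initial clinic visit".
- Section 7, pre-treatment visit: "After the clinical evaluation, the Study Coordinator will offer study enrollment, obtain consent and assign cohort based on randomization".
- Section 5.3: "The randomization assignment will be revealed to the unblinded study coordinator after consent". Clinicians learn the arm at the end of that clinic.

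Prior authorisation appears only in section 5.2. For the toxin it reads: "Prior authorization for drug injection will be done through normal clinical protocols as routine patient care". The same section says the same of retraining therapy. Neither sentence is tied to consent or to opening the allocation.

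On losses before treatment, section 7.3 states: "Participants that withdraw or are withdrawn prior to treatment will be replaced". It does not separate withdrawals before randomisation from those after it, and the only use it names for these patients' data is as baseline information. Section 8.1 specifies the 4-month model but defines no analysis set. Section 8.3 says only that dropout will be accounted for if necessary.

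**The concern.** Section 6.3 gives its own reason for the coverage rule: a patient who can receive only one of the two treatments is not really being randomised. To act on that reason, the trial must know before allocation that either treatment could be delivered. The written sequence has no such step.

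If a refusal of the assigned treatment comes after allocation, the patient decides whether to pay or leave knowing the arm. Whether the patient is lost then depends on which treatment was drawn and on which one the insurer refuses. Replacement restores the planned number treated and hides the loss, and with no analysis set defined, the comparison can be run on the patients who started treatment. The two groups compared at 4 months would then no longer be the groups that randomisation formed.

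**Working it through.** **1. Order of steps as written.** Clinical evaluation, offer, consent and assignment follow one another at the pre-treatment visit (section 7), with randomisation on the day of the initial visit (6.3). No coverage check is listed. Section 5.2 gives prior authorisation no position in this order. The time-point table in section 7 places pre-treatment measures between 6 weeks and 24 hours before treatment, so the plan allows a gap between that visit and treatment in which a refusal could arrive. Section 4.2 excludes earlier chemodenervation or retraining for synkinesis, so participants should have no earlier authorisation of these treatments for synkinesis to rely on.

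**2. The plan's own power figure.** Section 8.2 gives 18 per arm, SD 7.1, correlation 0.5, 10% loss and a 7-point difference. Two-sided alpha 0.05 is assumed, since none is stated.
- SD of change = 7.1 × √(2 × (1 − 0.5)) = 7.1.
- Evaluable per arm = 18 × 0.9 = 16.2.
- Standard error of the difference = 7.1 × √(2/16.2) = 2.49.
- Power = Φ(7/2.49 − 1.96) = 80.1%, or 77.5% with the t distribution.

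The stated figure of about 80% is reproduced, so this point does not rest on a sample-size error.

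**3. Size of a possible shift.** The documents give neither a refusal rate nor any link between coverage and response, so everything here is assumed. If k of the 18 patients allocated to one arm are lost and replaced, and their mean SFGS change would have differed by D points from that of the patients kept, the arm mean shifts by (k/18) × D.
- k = 1, D = 5: 5/18 = 0.28 points, which is 0.28/7 = 4% of the target difference.
- k = 2, D = 5: 10/18 = 0.56 points, which is 0.56/7 = 8%.

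**4. Sensitivity.** With loss rates p₁ and p₂ in the two arms and the same gap D in both, the difference between arms shifts by (p₁ − p₂) × D.

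| Loss in one arm / other arm | D = 3 | D = 5 | D = 7 |
|---|---|---|---|
| 5% / 0% | 0.15 | 0.25 | 0.35 |
| 10% / 0% | 0.3 | 0.5 | 0.7 |
| 20% / 0% | 0.6 | 1.0 | 1.4 |
| 20% / 10% | 0.3 | 0.5 | 0.7 |
| 30% / 0% | 0.9 | 1.5 | 2.1 |
| 10% / 10% | 0 | 0 | 0 |

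The sign depends on which arm loses patients and whether they would have done better or worse. The documents fix neither.

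**The case against.** The best defence is that the rule already precedes allocation. It governs enrolment, and enrolment and consent come before assignment. A check of insurance status before consent would fit section 6.3 as written. For a randomised patient to be lost this way, cover must look adequate at enrolment, the insurer must later refuse, the patient must be unable or unwilling to pay, and the patient must withdraw before treatment. For the toxin, section 5.2 also provides a second product where the insurer does not allow the first. Refusal of cover is not among the circumstances for early termination in section 7.3.

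Much of this stands, and it limits the point. A reader might infer any of the following, and the documents do not support them:
- **That anyone whose insurer declines a treatment is barred.** Section 6.3 allows self-payment.
- **That refusals necessarily become arm-dependent exclusions.** The documents do not say when coverage is checked. They leave the possibility open and do not show that it happens.
- **That refusal of the add-on treatment biases the primary comparison.** It would act in months 4 to 8, after the baseline-to-4-month contrast in section 8.1. The Summary (Aim 1) also names eight months for SFGS, so it could affect that time point.
- **That absence from section 4.2 leaves the rule without force.** Section 6.3 states the rule, so its absence from the list is editorial.
- **That the shift could take a third of the target.** That needs 4 of 18 lost in one arm, none in the other, and a 10-point gap: 4/18 × 10 = 2.2 points, or 32% of 7. A 10-point gap is 10/7.1 = 1.4 SDs of change. Nothing in the documents supports that combination.

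The defence does not close the gap. A check of insurance status is not an authorisation decision, and neither is required before allocation. The second toxin product does not help where toxin treatment in general, or retraining therapy, is refused. Section 7.3 lets participants withdraw for any reason, and its replacement rule makes no exception for those already randomised.

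**Conclusion.** The point holds as a gap in procedure that should be closed, not as a demonstrated bias. As written, the plan allows a randomised patient to be lost for a reason tied to the assigned treatment and then replaced. The replacement wording is the more important half, because it applies to any loss between allocation and treatment, whatever the cause.

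Size and direction are unknown. Under the modest assumption in the working (1 or 2 of 18 replaced in one arm, none in the other, a 5-point gap), the shift of 0.28 to 0.56 points is about 11% to 22% of the standard error of 2.49. It would be nil if losses and gaps were equal in the two arms, and larger if refusals were frequent and confined to one arm.

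**What to change.** 1. **Sections 7.3 and 8.1.** Limit replacement to patients who withdraw before randomisation. State that all randomised patients are analysed in their assigned arm. Seek the 4-month SFGS video, with the patient's agreement, from those who do not start the assigned treatment. Section 2.1 describes video as part of routine visits, and section 7.3 keeps withdrawn patients under standard care, so this is feasible for many of them.
2. **Sections 6.3 and 5.3.** Require coverage, or agreement to self-pay, to be confirmed for both treatments before the coordinator opens the allocation. Allow randomisation after the initial visit where needed. This also reconciles same-day randomisation with the route in section 6.3 under which an absent coordinator phones the patient within a week. A cross-reference in section 4 would be tidy.

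**Cost.** Besides the rewording, there may be a delay or a second contact before allocation. The documents do not say how long authorisation takes, and section 8.2 needs 36 of about 72 eligible patients in a year, so there is little slack. Not replacing late withdrawals means slightly fewer treated patients. If those who do not start supply no 4-month score, power falls from 80.1% to 79.1% with 5% lost in one arm, or 78.0% with 10%. If they do supply one, the numbers are kept, but patients not given the assigned treatment may dilute the contrast. Confirming coverage first turns known coverage failures into screen failures before randomisation and should make both cases rare.
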